## **10.0 Study Design / Methods**

A target of 45 dual users across South Carolina will be recruited through various media outlets. Advertising will solicit vapers motivated to quit. Dual users will consent to be screened online for study eligibility, including potential for pregnancy. Pregnancy status and health conditions contraindicated to NRT (past month myocardial infarction, current cardiac arrhythmia, current angina, uncontrolled vascular disease, or medical conditions in which consumption of phenylalanine is contraindicated, including Phenylketonuria [PKU] and allergy to phenylalanine) will be ascertained via self-report on the online pre-screener. In addition, we will ask participants if they are sexually active and if they are using any type of contraceptive method (with a list of available options). If female participants are deemed eligible (i.e., not pregnant and not engaging in unprotected sex) and schedule an intake, they will be mailed a pregnancy test. They will be told they will not complete the test until after they have consented to the study and agree to continue. During consent, we will discuss the exclusion criteria for pregnancy, as well as review risks of medication use as it pertains to pregnancy and the aforementioned medical conditions.

If the participant qualifies, research staff will schedule a time to complete the interview and baseline assessment battery. Following consent, during the initial intake assessment, we will conduct the pregnancy test on applicable participants. If the test is negative, we will continue with the rest of the study procedures. Participants will then be randomized to study arm (Arm A (21mg patch, qd + 4mg lozenge prn [minimum of 5 & up to 20 per day]); Arm B (21mg patch + 14mg patch qd + 4mg lozenge prn [minimum of 5 & up to 30 per day]), or Arm C (2X21mg patches qd + 4mg lozenges prn [minimum of 5 & up to 40 per day]). Participants will be provided with a 28-day supply of NRT by mail and a self-help booklet (which includes instructions for medication use) and instructions to select a target quit date within 1 week. Research staff will contact the participants upon receipt of the materials and obtain the

target quit date. Participants in both groups will receive a brochure with information for contacting the SC QuitLine. During the 28-days of treatment, participants will be sent daily monitoring surveys asking about e-cigarette use, cigarette smoking, NRT, and quit attempts during the previous day. One month following the receipt of the materials, participants will complete an assessment battery. All assessment procedures will be completed via approved remote data collection platforms (e.g. REDCap). Participants will have the option to receive all study-related surveys (through REDCap) via text message or via email. No identifying information will be included on the texts/emails.

**Randomization.** Participants will be randomized to one of the following NRT conditions: Arm A (21mg patch, *qd* + 4mg lozenge *prn* [minimum of 5 & up to 20 per day]); Arm B (21mg patch + 14mg patch *qd* + 4mg lozenge *prn* [minimum of 5 & up to 30 per day]), or Arm C (2X21mg patches *qd* + 4mg lozenges *prn* [minimum of 5 & up to 40 per day]). Randomization to the intervention groups will be stratified on dependence score as follows: Participants will complete both the Roswell ENDS Nicotine Dependence Scale (Roswell eND; e-cigarette dependence) and the Fagerström Test for Nicotine Dependence (FTND; smoking dependence). Both scales have score ranges from 0 (no dependence) – 10 (high dependence). Consistent with cutoffs for the Roswell eND scale, participants will be stratified by low dependence (0-5) or high dependence (6-10) based on their highest score on either scale.

**Treatments.** All treatment procedures will be conducted remotely (e.g., online, through mail).

**Intervention:** Following randomization, participants will be instructed to select a quit day (Day 0) within the next week at which time they will commence using NRT. Participants will be sent a supportive text message reminder on that date (“*Today is your quit date! Make sure to use your medications and written materials to help you. You got this!*”).

**NRT medications.** Following consent, participants randomized to the combined intervention will be mailed their 28-day supply of NRT. All participants will be encouraged to use the highest dose sent to them based on their randomization. A specific emphasis will be made on instructing participants to use both patches and lozenges concurrently. We will allow participants to engage in dose reductions naturally if they feel they need to, which will be captured through the daily surveys. Although this medication has not been formally tested for ENDS cessation, with the exceptions of our small pilot studies, it is the first line treatment for cigarette cessation. For this reason, we believe it is a safe and acceptable pharmacotherapy to use for this intervention. We will monitor adverse events.

**Behavioral Support.** A brief, informational booklet will be provided to participants that discusses how to plan and engage in a quit attempt of all tobacco products used. This will be adapted from currently used treatment manuals utilized by the MUSC Tobacco Treatment Program with clinical patients. This booklet will also provide information regarding the SC QuitLine, a freely available public service that provides tobacco cessation counseling and medication over the phone or through mobile/web platforms. Participants will be informed about the services the QuitLine offers as well as how to contact this service.

**Daily Monitoring.** During the 28-days of treatment, all participants will be sent daily monitoring surveys (described later). All assessment procedures will be completed via approved remote data collection platforms (e.g., texting via Redcap). To increase retention, we will call participants who do not respond for  $\geq 3$  days.

**Follow-up.** At the end of treatment (Day 28), research staff will contact the participant to complete an assessment battery. Four weeks after this (Day 56), a final follow-up assessment battery will be administered. Those who report abstinence from smoking will be mailed a remote carbon monoxide monitor (iCO) to complete and return. To increase retention, surveys will be sent via text and email, and we will call participants who do not respond within 1 week.

**Measures.** Dual users who enroll in the study will first complete an assessment battery.

## Assessments

[figure not shown]
- Demographics (Baseline): Demographics will include sex, gender, sexual orientation, race, ethnicity, age, income, education, marital status, and health insurance status.
- E-cigarette Use History (Baseline): At baseline participants will report e-cigarette use history (length of e-cigarette use, device, flavor, why they started, past quit attempts), current weekly use rates (days per week, estimated times per day, estimated puffs per day, length that a cartridge/refill lasts) and details about their specific product typically used (type, flavors, nicotine content, size of cartridge/refill).
- Cigarette Use History (Baseline): Participants will report retrospective (lifetime) and current weekly (past 7-day) use of cigarettes, including length of time smoking, brand smoked, cigarettes per day, and quit attempts.
- Motivation and Confidence to quit (Baseline, Days 28, 56): Participants will be asked to rate on a scale of 1-10, 10 being highest, their level of motivation and confidence in their upcoming quit attempt. If still using ENDS/smoking at end of treatment or follow-up, this will be re-assessed.
- Expectancies (Baseline). Expectancies for e-cigarette use will be measured using the Short Form Vaping Consequences Questionnaire (S-VCQ) and expectancies for smoking will be measured using the Smoking Consequences Questionnaire (SCQ).
- Dependence (Baseline, Days 28, 56). Participants will complete the Roswell eND Scale, which has been validated to measure dependence on individuals seeking to quit ENDS use, as well as the Fagerström Test of Nicotine Dependence (FTND).
- Daily monitoring survey (Treatment [Days 1-28]): In addition to the primary endpoints above, daily surveys will ask about the previous day: attempts to quit e-cigarettes/smoking, cravings to vape (Vaping Craving Questionnaire), cravings to smoke (Questionnaire of Smoking Urges), and NRT use (number of patches and/or lozenges used). Participants will also be asked if they used the supportive booklet or engaged with the Quitline, and length of each interaction.
- Withdrawal (Treatment [Days 1-28]): Symptoms of withdrawal will be measured using the Brief Wisconsin Inventory of Smoking Dependence Motives (WISDM) scale.
- Timeline Follow-Back (TLFB; Days 29-56): On Day 56, a study staff member will conduct a TLFB assessment to capture vaping, smoking, and NRT use over the previous month.
- Carbon Monoxide (Day 28, Day 56): Participants who report abstinence from cigarette smoking will be sent an iCO to provide samples at each timepoint. TLFB data will be used to cross-reference self-reported product use.

Participant compensation. Participants will be compensated \$25 for each the baseline, end of treatment, and follow-up assessments. Participants can earn up to \$60 more for daily survey completion (biweekly payments as follows: \$10 for 1-4 completed, \$15 for 5-6, \$20 for 7-11, \$25 for 12, \$30 for 13-14). Participants will be compensated with \$20 for each CO sample provided (up to 2). To improve retention, participants who complete >85% (27 out of 31) of assessments will receive a bonus payment of \$25. The maximum that someone in this study can earn if they complete all aspects of the study is \$200. Participants will be offered electronic payments via ClinCard.

# of Assessments Completed in 2 weeks	Amount paid (Bi-weekly)
1-4	\$10
5-6	\$15
7-11	\$20
12	\$25
13-14	\$30

## 11.0 Data Management

Power analyses were performed using PASS 2022 v 22.0.4. Forty-five subjects will be randomly allocated 1:1:1 to treatment arm (A, B or C) using permuted block randomization with block sizes of 3 or 6. Randomization will be stratified by level of dependence (low vs high). The primary endpoint is a binary indicator of abstinence (yes or no) measured daily for 28 (56) days from treatment initiation. Generalized estimating equations (GEEs) will be used to model the log odds of abstinence as a function of treatment arm. Separate models will be fit to evaluate abstinence in the first 28 or 56 days. Following best practice for covariate adjustment, level of dependence (stratification variable) will be included as a model covariate. We will assume a compound-symmetric working correlation structure, but all final estimates and inference will be based on the robust sandwich estimator. Finally, we will conform with the intention-to-treat principle and therefore anticipate no issues secondary to missing data. The probability of abstinence in each treatment arm, differences in abstinence probabilities between treatment arms, and corresponding 90% confidence intervals will be estimated based on the fitted model. These estimates will then be used to construct model-based point and interval estimates of the average number of days abstinent in the first 28 (56) days from treatment initiation by multiplying by a factor of 28 or 56 as appropriate. As an additional analysis, we will include time (continuous) and arm-by-time interaction to evaluate temporal trends. Finally, we will investigate gender-related treatment effect heterogeneity by including sex and arm-by-sex interaction terms. However, sample size is small, and we consider such models to be purely exploratory. **Fig 1** shows the power to detect a difference in the probability of abstinence between two groups of size 15 measured at 28 timepoints, where the probability of abstinence in group 1 is 10% (**Fig 1A**) or 15% (**Fig 1B**), the probability of abstinence in group 2 ranges from 30% to 50%, and inference is based on GEE Wald tests with two-sided  $\alpha = 0.1$ . Null abstinence rates ranging from 10 to 15% are justified based on preliminary data presented in this application. With no preliminary data to estimate the intra-cluster correlation (ICC), we considered a broad range of ICC values (0.2 to 0.5).

**Fig. 1** Power to detect a two-group difference in abstinence ( $P_2 - P_1$ ) for (A)  $P_1 = 0.1$  or (B)  $P_1 = 0.15$  across ICC values ranging from 0.2 to 0.5.

*All studies:*

Several steps will be taken to safeguard the confidentiality of subjects and their data. From the original data collected from participants, any identifying information will be removed, put into another file (described later), and all participants will be given a study number. Coded data will be stored in digital databases (Box folder). The names of participants will not be associated with this data and assessments will be maintained according to participant study number. A master list connecting participant study numbers to participant names and other identifying data will be kept in a locked file cabinet where it can only be accessed by senior level project staff. OnCore records will be maintained for each participant. Any information published as a result of the study will be such that it will not permit identification of any participant.

Right to privacy for participation in this research will be protected through coding of data and proper storage of research records. Consistent with mandated reporting requirements for health providers, we advise participants that in the case of child abuse or neglect, threat of injury to self or others, or intention to destroy property, that we may need to intervene and report that information to the proper authorities. Subjects will be informed of this limit to confidentiality as it is stated in the informed consent document.

The data will be stored in a locked room for 6 years after the final data is collected. The PI and the research staff will have access to PHI. Organizations that have a responsibility for protecting human participants, including the MUSC IRB, may have access to subjects' records containing PHI. Additionally, the funding source may have access to subjects' records containing PHI.

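### The primary GEE intervals use a robust sandwich estimator with 15 participants per arm and no stated small-sample correction; on the ordinary reading, 90% intervals for arm differences cover about 86–88%

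*Combined protocol and SAP*

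**What the plan says.** Section 11.0 (Data Management) models the log odds of daily abstinence by GEE, with treatment arm and dependence level as covariates and a compound-symmetric working correlation. On the variance it says that "all final estimates and inference will be based on the robust sandwich estimator".

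From this model, "differences in abstinence probabilities between treatment arms, and corresponding 90% confidence intervals will be estimated based on the fitted model". The estimates are then multiplied by 28 or 56 to give "model-based point and interval estimates of the average number of days abstinent in the first 28 (56) days from treatment initiation".

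The only statement about the form of the test is in the power calculation, for two groups of 15, where "inference is based on GEE Wald tests with two-sided" alpha of 0.1. The section's one remark that the sample is small concerns the exploratory sex-interaction models. Nowhere do the documents name a bias-corrected variance, a t or F reference, degrees of freedom, or a permutation or bootstrap method.

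**The concern.** Treating the participant as the cluster is right. But the ordinary sandwich estimator is justified for many clusters, and here there are 45 in all and 15 per arm. It is built from fitted residuals, which are on average smaller than the true errors, so it underestimates the variance. A normal reference then ignores the uncertainty in that variance estimate. Both faults narrow the interval.

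Between-arm differences with 90% intervals are how the plan reports Aim 1, and the Aims section says that the data will inform a later trial application. The plan has already chosen a lenient 10% error level; an unrecognised 12–14% would overstate the precision carried into that application. If the variant stays unstated, it could also be chosen after the data are seen.

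**Working it through.** **Inputs from the documents.** Three arms of 15 (sections 5.0, 6.0 and 11.0). Logit GEE with four parameters: intercept, two arm terms and dependence (11.0). Abstinence of 10% or 15% in one group against 30% to 50% in the other, intra-cluster correlation (ICC) 0.2 to 0.5, two-sided alpha 0.10 (11.0). Missing days count as not abstinent (4.0), so every participant contributes the same number of days.

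**Stated figure.** The text gives no numerical power, and the curves of Fig. 1 are not in the supplied copy, so there is nothing to reproduce or contradict. As a check of the set-up, take 10% against 30% at ICC 0.5:
- variance factor: (1 + 27 × 0.5)/28 = 0.518
- SE of the difference: √[(0.09 + 0.21) × 0.518/15] = 0.102
- power: Φ(0.20/0.102 − 1.645) ≈ 0.63; the same formula gives 0.91 at ICC 0.2.

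**Analytic check.** For two groups of 15 and normal-theory data, the uncorrected variance is too small by the factor 14/15, and the statistic properly follows t on 28 df:
- effective critical value: 1.645 × √(14/15) = 1.589
- coverage: 2 × T₂₈(1.589) − 1 = 87.7%.

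This is before skewness or the extra covariate is allowed for.

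**Simulation of the planned model.** There were 10,000 trials in each of 40 settings. Coverage was pooled over the B−A and C−A differences in standardised probability, with delta-method standard errors. Monte Carlo error is about 0.3 points. The shape of the daily data, the share with high dependence and the size of the dependence effect are not in the documents; they were assumed and varied. Trials without a finite fit (0–1.4%) were excluded. The GEE fit and its ordinary robust standard errors matched a standard software implementation.

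| Settings | Coverage, ordinary sandwich with z |
|---|---|
| Equal arms, 10% or 15% | 86.6–87.6% |
| 10% or 15% vs 30% or 50% | 86.5–87.2% |
| 56 days | 86.7–87.2% |
| Logit-normal instead of beta-binomial data | 86.4–87.2% |
| Dependence odds ratio 0.5 | 86.4–86.8% |
| Stratified, "permuted block randomization with block sizes of 3 or 6" | 86.5–87.6% |

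Under the null, the test of the difference rejects in 12.4–13.6% of trials instead of 10%.

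**Source of the shortfall.** The mean uncorrected standard error is 0.902–0.950 of the true standard deviation of the estimated difference. With the Kauermann-Carroll correction the ratio is 0.953–0.997. Mean coverage over the 40 settings:

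| Method | Mean coverage |
|---|---|
| Ordinary sandwich, z | 86.8% |
| Ordinary sandwich, t(41) | 87.7% |
| Kauermann-Carroll, z | 88.8% |
| Kauermann-Carroll, t(41) | 89.6% (range 88.9–90.4%) |

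**Replication.** A separately coded simulation over a similar grid, which also included all arms at 30%, gave 86.0–88.3% for the ordinary method and about 89–91% for Kauermann-Carroll with t.

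**The case against.** The strongest reply is that this is an unspecified detail, not a demonstrated error. Bias-corrected forms are also sandwich estimators, the power sentence names neither z nor t, and no software is named for the GEE analysis. That is correct, and the finding is conditional for this reason. But the ordinary reading of the stated method gives intervals that are too narrow, and one clause settles the matter either way.

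A second objection is size. The shortfall is about 2.4 to 3.6 points in a study that calls Aim 1 preliminary, and in one example the half-width moves by only about a quarter of a day in 28. This stands as a limit on importance. It does not remove the reason for a cheap correction to the primary analysis.

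Third, Kauermann-Carroll is not the only adequate choice: Mancl-DeRouen with z covered about 90–92%. That also stands. What matters is to name one sound method in advance.

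Fourth, the result holds at the plan's assumed rates ("Null abstinence rates ranging from 10 to 15% are justified"), yet no dual user in the pilot quit smoking. If every arm were at 5% with ICC 0.5 (an assumption), uncorrected coverage was 91.2%, the correction raised it to 94.7%, and 17% of trials had an empty arm or no finite fit. At 3% against 15% with ICC 0.5, coverage was 84.4%, and 86.8% after correction. At such rates sparse data is the larger problem, and this correction does not solve it.

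**Conclusion.** The concern holds, as a modest defect that should be fixed. If the sandwich is the ordinary one with a normal reference, nominal 90% intervals for between-arm differences in abstinence probability, and for differences in days abstinent, cover about 86–88% at the plan's rates and ICCs. The result varied little with the data shape, the dependence assumptions, the stratified randomisation or the length of follow-up.

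The conclusion is limited to the between-arm contrast, to the ordinary reading of the text, and to abstinence rates in the range the plan assumes. It contradicts no stated power.

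**What to change.** Keep the GEE, its point estimates and the planned contrasts. Add one clause to section 11.0: standard errors use the Kauermann-Carroll bias-corrected sandwich, and 90% intervals and tests for between-arm differences are referred to t with degrees of freedom equal to participants analysed minus model parameters (45 − 4 = 41).

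No new data are needed. With participant-level covariates and equal numbers of days, the correction divides each participant's residual total by √(1 − leverage). Mean leverage is 4/45 = 0.089, so standard errors grow by about 1/√(1 − 0.089) = 1.048. The t(41) critical value of 1.683 against 1.645 adds a factor of 1.023, and 1.048 × 1.023 ≈ 1.07. This shortcut does not extend to the additional arm-by-time model, which needs the general form of the correction.

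The simulated cost, at ICC 0.5 unless stated:
- Mean half-width, 10% in both arms: 3.37 to 3.64 days of 28 (+8%).
- Mean half-width, 10% vs 30%: 4.46 to 4.79 days of 28 (+7%).
- Apparent power, 10% vs 30%: 66% to 61%, and 91% to 89% at ICC 0.2. The ordinary figures are flattered by the excess type I error.

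As a separate matter, build single-arm intervals on the logit scale, back-transform them and label them approximate. For an arm at 10–15% they cover only 81–88% even with this correction, mainly because of skewness.

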reporting e-cigarette use and smoking at end of treatment (EOT) and 1-month follow up. In 6 months, we enrolled 30 participants; 24 (80%) of whom completed the EOT survey and 18 (60%) who completed follow-up. As shown in Table 1, following treatment, 33.3% (6/18) of the intervention group that received NRT was able to quit vaping whereas 0% in the control group did (3-day point prevalence). Notably, no dual users quit smoking; that is, some discontinued their e-cigarette use but continued to smoke. Some dual users were able to reduce their e-cigarette use and/or smoking, and only one had increased their smoking. Another important observation from this study was that individuals who achieved abstinence from vaping self-reported using NRT more than those who were not abstinent (see Table 2).

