### 4.0 Study Endpoints.

#### Primary Endpoint:

*Days of dual use abstinence (Day 28, Day 56):* The primary outcome of interest is the number of days participants self-report abstinence from both e-cigarettes and smoking. These data will be derived from daily surveys that query about the previous day's e-cigarette use (yes/no, estimated number of times

vaped, estimated amount of cartridge/refill used) and cigarette smoking (yes/no overall, number of cigarettes smoked). Non-responders and missing data will be coded as not abstinent.

Secondary Endpoints:

**Reduction (Day 28, Day 56):** In addition to number of days of complete dual product abstinence, we will use baseline and daily survey data (described above) to calculate the reduction of e-cigarette use and smoking between groups from baseline to end of treatment.

**Safety (Day 28):** To further assess differences in acceptability and response to the treatment doses, adverse events between groups will be evaluated. NRT side effects will be captured during daily diary assessments using the Systematic Assessment for Treatment Emergent Events (SAFTEE).

**Feasibility/Acceptability (Day 28):** Feasibility and acceptability endpoints will be determined by the proportion of eligible subjects able to be contacted who subsequently enroll, the proportion of enrolled subjects who complete the Day 28 survey, and the proportion of enrolled subjects who complete ≥80% of their daily surveys during the treatment period. Participants will report satisfaction and helpfulness of the intervention at the end of treatment (Day 28).

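### The planned time trend ignores the switch from daily diaries to one recall interview and counts unreported days as use, so falling response can look like falling abstinence

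*Combined protocol and SAP*

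**What the plan says.** Section 11.0 defines the modelled outcome: "The primary endpoint is a binary indicator of abstinence (yes or no) measured daily for 28 (56) days from treatment initiation". On windows it says "Separate models will be fit to evaluate abstinence in the first 28 or 56 days". The additional analysis then follows: "we will include time (continuous) and arm-by-time interaction to evaluate temporal trends". It does not say whether the time terms go into the 28-day model, the 56-day model or both; both is the natural reading. No term for period or data source is mentioned.

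The data sources are set out in section 10.0. Under Assessments, the daily monitoring survey is a treatment-period instrument for Days 1-28. Days 29-56 are covered by a timeline follow-back (TLFB): "On Day 56, a study staff member will conduct a TLFB". Section 4.0, however, says of the Day 28 and Day 56 endpoint "These data will be derived from daily surveys", although those surveys stop at Day 28. The TLFB is therefore inferred to supply Days 29-56, as the only instrument that covers them.

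On missing data, section 4.0 states "Non-responders and missing data will be coded as not abstinent". Section 11.0 expects no missing-data problem and plans no sensitivity analysis for it.

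**The concern.** A slope over time can be read as a change in abstinence only if abstinence is ascertained in the same way along the time axis. Here it is not, for two separate reasons.

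- **Change of instrument.** Days 1-28 rest on up to 28 previous-day reports per person. Days 29-56 rest on one interview with recall of up to four weeks, and missing it loses all 28 days. This affects only a 56-day trend.
- **Coding of unreported days.** Each such day enters the model as an observed day of use. If response falls over time, recorded abstinence falls with it. This affects both windows.

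The trend model is the only planned analysis of whether abstinence builds or fades and whether that differs by dose. A decline that came from response could be read as relapse and carried into the design of the later trial that section 1.0 has in view.

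**Working it through.** The plan gives no figure for the trend analysis, so there is nothing to reproduce.

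**Inputs from the documents**
- 45 participants, 15 per arm; exchangeable logistic GEE with robust variance; two-sided alpha 0.1; ICC considered from 0.2 to 0.5 (section 11.0).
- Pilot completion: "24 (80%) of whom completed the EOT survey and 18 (60%) who completed follow-up" (section 2.0, Proof-of-concept), that is 24/30 = 80% and 18/30 = 60%. These are survey completion figures from a mixed group of mono and dual users. They serve here only as a proxy for diary and TLFB response.

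**Assumptions**
- True abstinence is constant at 30% in every arm (the lower end of the plan's 30-50% range for group 2).
- Missingness is unrelated to use.

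**Step 1: size of the coding error.** Let r be the share of days reported and q the true abstinence rate on unreported days. Recorded abstinence falls short of the truth by (1 − r) × q.

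| q | r = 0.80 | r = 0.60 | Extra shortfall in the second window |
|---|---|---|---|
| 0.30 | 0.06 | 0.12 | 6 points |
| 0.15 | 0.03 | 0.06 | 3 points |
| 0 | 0 | 0 | none |

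With q = 0.30, recorded abstinence is 0.30 × 0.80 = 24% and then 0.30 × 0.60 = 18%. With q = 0 the coding is right.

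**Step 2: effect on the slope.**
- 56 days, 24% then 18%: the step has odds ratio (0.18/0.82)/(0.24/0.76) = 0.695, or −0.364 on the log scale. A least-squares line through a step at the midpoint has a total change of 1.5 times the step. That gives exp(1.5 × −0.364) = 0.58. The simulated GEE gave about 0.60.
- Days 1-28, diary completion sliding from 100% to 80%: recorded abstinence goes from 30% to 24%, with odds ratio (0.24/0.76)/(0.30/0.70) = 0.74. Simulation gave 0.73-0.75.

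**Step 3: how often a false trend is declared.** The GEE was simulated with 200 to 500 trials per setting (standard error about 2 to 4 points), with the dependence covariate omitted. One set drew days independently within person at ICC 0.4. Another let part of the within-person correlation be day-to-day persistence.

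| Setting | Independent days | With persistence |
|---|---|---|
| Time trend, complete reporting | 10-15% | about 12% |
| Time trend, 56 days, 80% then 60% | 47-49% | 35-37% |
| Time trend, Days 1-28, 100% sliding to 80% | 55-57% | 19-26% |
| C-versus-A by time, TLFB 11/15 in A and 7/15 in C | 23-26% | 15-20% |

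The comparison for the last row is 10-16% with complete reporting. The slope odds ratios hardly move with persistence; the rejection rates do.

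The pattern of loss matters too. With permanent dropout at a random diary day (20% missing by Day 28, 40% by Day 56, ICC 0.35, independent days, 150 runs), false time trends appeared in 41% of 28-day and 92% of 56-day fits. A few 56-day fits did not converge and were counted as non-significant. Because this loss was equal across arms, the 56-day C-versus-A by time term stayed near nominal at 11%.

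**Step 4: does the remedy work?** With independent days, adding a Day 29+ term in the 80%/60% setting brought the false time trend back to about 12-13%. Fitting reported days only in the sliding-diary setting brought it to about 10%. No result after the change is available for the unequal-arm setting.

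**The case against.** The strongest reply is that little hangs on this model. It is an additional analysis, and no hypothesis, endpoint or power statement uses a time slope. The remark in section 11.0 that small samples make such models exploratory directly follows the sex-interaction sentence, but can fairly be read to cover the time model as well. Scoring non-response as use is a deliberate rule, and it is correct if non-reporters were using. Section 10.0 also provides calls after three or more silent days, payments and a completion bonus. Section 4.0 makes diary and Day 28 completion feasibility endpoints.

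Much of this stands, and it keeps the priority low. It does not remove the point. Retention effort may reduce missingness but changes neither the coding nor the instrument. The feasibility endpoints are not broken down by arm and week, so a reader could not judge how much of a slope is response.

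Three stronger readings are tempting and not supported:
- *A stable abstinence rate will produce a significant decline.* Under the assumed losses that happens in some simulated trials, not all, and not through the coding if q is 0.
- *The analysis will produce a false dose-by-time effect.* That needs a response gap between arms that changes over time. The 11/15 versus 7/15 split is assumed, and the inflation is modest even then.
- *Recall will overstate abstinence after Day 28.* The documents give no size or direction for recall error, so none is claimed.

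**Conclusion.** The point holds for the additional trend analysis. If some unreported days were truly abstinent, falling response biases the time slope downward. Over 56 days the change of instrument is also inseparable from any change in behaviour at Day 29.

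Under constant 30% abstinence, missingness unrelated to use, and 80% then 60% reporting, the 56-day slope odds ratio is about 0.6 and a false trend is declared in about 35-50% of trials at alpha 0.1. For Days 1-28 with diary completion sliding to 80%, the figures are about 0.73-0.75 and 20-57%. The ranges reflect mainly how persistent abstinence is from day to day, which the documents do not give. Arm-by-time inflation is modest: about 15-26% against 10-16% with complete reporting.

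A reader might infer that the primary 28-day and 56-day arm comparisons are undermined. This check does not address them, and the primary coding need not change. The point is worth considering rather than essential.

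**What to change.** In section 11.0:
- State which window the time and arm-by-time terms apply to.
- For Days 1-28, keep the planned trend with missing days scored as not abstinent. Beside it, show the same model fitted to reported diary days only, stating that this version assumes uninformative missingness.
- For any 56-day trend, use a period indicator (Days 1-28 diary, Days 29-56 TLFB) with arm-by-period terms instead of a single slope. State that the Day 29 step cannot be separated from the change of instrument.
- Report the percentage of days reported by arm and week next to the trend, and label the trend results exploratory.

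In section 4.0, name the TLFB as the source for Days 29-56 if that is the intention.

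The cost is SAP wording and one or two extra fits on data already being collected. The 56-day analysis loses its single-slope summary. If a slope is kept beside the period terms, the model grows from 7 coefficients (intercept, 2 arm, dependence, time, 2 arm-by-time) to 10 (adding period and 2 arm-by-period). That is a lot for 45 participants and a further reason for the exploratory label.
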